11.1.3 PK/PD-subset Sample Concentration Data, PD analytes

Blood samples for PD assessment in TransCon hGH Cohort 1 PK/PD Population will be collected at Visit 3 (Week 13) at following time points: Predose (defined as time zero), 8, 12, 16, 24, 36, 48, 72, 96, 120 and 168 hours post dose.

Below are the time windows by design for PD sample collection:

- Predose (-0.5 hour): within \pm 30 minutes
- 8 to 48 hours post-dose: \pm 1 hour
- 72 to 168 hours post-dose: \pm 3 hours

The individual serum concentration versus actual time data will be used to derive the PD parameters.

Blood samples will be processed to serum for quantification of insulin-like growth factor-1 (IGF-1) and insulin-like growth factor binding protein-3 (IGFBP-3). The lower limit of quantitation (LLOQ) for each of the PD analytes are as follows:

- IGF-1: 20.0 ng/mL
- IGFBP-3 150.0 ng/mL
- SD-scores for IGF-1 and IGFBP-3 will be calculated by Laboratorium für Klinische Forschung GmbH, Germany, based on absolute serum concentration data applying published IGF-1 and IGFBP-3 age and gender-specific Standard Deviation Score (SDS) reference ranges^{[11],[12]}. If a sample concentration is below the LLOQ, the concentration will be set to the LLOQ for calculation of SD-score.

The calculation of the SDS will be performed using the following formula^[13]:

$$SD - Score = \frac{([\text{serum conc}]/M)^L - 1}{S * L}$$

[serum conc]: IGF-1/ IGFBP-3 serum concentration in ng/mL

M = Median reference value age- and gender specific^{[11],[12]}

L = Lambda (Skewness)^{[11],[12]}

S = Sigma (Standard Deviation)^{[11],[12]}

Individual baseline adjusted IGF-1 and IGFBP-3 concentrations will be calculated as follows:

$$C_{baseline-corrected,t} = C_{measured,t} - C_{predose}$$

where $C_{baseline-corrected,t}$ is the baseline adjusted concentration at a given time point; $C_{measured,t}$ is the measured concentration in the sample at a given time point and $C_{pre-dose}$ is the baseline at predose Visit 1.

Baseline corrected SD-score will be calculated as follows:

$$SDS_{baseline-corrected,t} = SDS_t - SDS_{predose}$$

where $SDS_{baseline-corrected,t}$ is the baseline corrected concentration at a given time point; SDS_t is the calculated SDS based on the reference range for the given sample and $SDS_{predose}$ is the baseline value at predose (Visit 1).

All serum concentration values BLQ will be set to lower limit of quantification when calculating summary statistics; baseline-corrected values which are negative will be reported as negative values.

Absolute and baseline-corrected serum concentration data will be listed and summarized by time point for using descriptive statistics (number of subjects, arithmetic mean, arithmetic SD, arithmetic CV, median, minimum, and maximum, and geometric mean and geo CV, if applicable). Concentrations/ SD-scores will be reported in the same format as the original serum concentration (1-decimal place) and SD-score (2-decimal places) raw data. Descriptive statistics will be reported to 3 significant figures.

IGF-1 and IGFBP-3 arithmetic mean serum concentration (absolute and baseline-corrected) and IGF-1 and IGFBP-3 SD-score (absolute and baseline-corrected) versus nominal time profiles will be presented in figures on both linear and semi-logarithmic (if applicable) scales. IGF-1 and IGFBP-3 individual serum concentration data (absolute and baseline-corrected) and IGF-1 and IGFBP-3 SD-score (absolute and baseline-corrected) versus actual time profiles will be presented in figures on linear scale.

11.1.3.1 Pharmacodynamic Parameters

All parameters will be calculated using Phoenix WinNonlin (Version 6.4 or higher). The PD parameters for IGF-1, IGFBP-3 and IGF-1, IGFBP-3 SDS* (absolute and baseline-corrected) to be calculated include, but are not limited to, the following:

Parameter	Description
AUEC ₀₋₁₆₈	Area under the efficacy curve, AUEC from time 0 to 168 hours after dosing
E _{max}	Maximum observed response
TE _{max}	Time to achieve maximum observed response

*Note: Only E_{max} and TE_{max} will be reported for IGF-1 SDS and IGFBP-3 SDS.

Actual collection times post-dose will be utilized in the calculations of the PD parameters.

For the calculation of PD parameters all serum concentrations that are BLQ will be set to lower limit of quantification. Baseline-corrected concentrations which are negative will also be included in the calculation. No concentration estimates will be imputed for missing sample values. Any sample with a missing value will be treated as if the sample had not been scheduled for collection and will be ignored when calculating mean concentrations or PD parameters.

Calculation of AUEC for baseline-corrected IGF-1 and IGFBP-3 will include negative peak areas if occurring, i.e. the net area will be reported.

The absolute and baseline-corrected PD parameters of IGF-1, IGF-1 SDS and IGFBP-3 will be summarized for each treatment using descriptive statistics (number of subjects, arithmetic mean, 95% CI of arithmetic mean, arithmetic SD, arithmetic CV, median, minimum, maximum, and geometric mean and geo CV, if applicable). For the display of PD parameters in tables and listings, the PD parameters and descriptive statistics will be presented with 3 significant figures.

12. References

- [1] US Federal Register. (1998) International Conference on Harmonization; Guidance on Statistical Principles for Clinical Trials. Department of Health and Human Services: Food and Drug Administration [Docket No. 97D-0174]. Federal Register Volume 63, Number 179, pages 49583-49598. September 16, 1998.
- [2] ASA. (2016) Ethical Guidelines for Statistical Practice. Prepared by the Committee on Professional Ethics, April 2016. <http://www.amstat.org/about/ethicalguidelines.cfm>
<http://www.amstat.org/about/ethicalguidelines.cfm>
- [3] RSS. (2014) The Royal Statistical Society: Code of Conduct, 2014. .
<http://www.rss.org.uk/Images/PDF/join-us/RSS-Code-of-Conduct-2014.pdf>

13.1 Planned Table Descriptions

The following are planned summary tables for protocol TransCon hGH CT-301. Tables will be numbered according to the nomenclature used to support the clinical study report (CSR) when the Premier Research CSR template is used. However, the table numbering structure can be modified per the sponsor's request to meet compatibility with the sponsor's CSR template.

13.1 Demographic Data Summary Tables and Figures (To include demographics, baseline characteristics, disposition and exposure tables: Number as 14.1.1.)

Table 14.1.1	All Subjects	Study Populations
Table 14.1.2.1	All Subjects	Screen Failures
Table 14.1.2.2	All Randomized Subjects	Subject Disposition
Table 14.1.3.1	ITT/PP	Demographics and Baseline Data
Table 14.1.3.2	ITT/PP	Birth Data
Table 14.1.4.1	ITT/PP	Medical History by SOC and Preferred Term
Table 14.1.4.2	ITT/PP	Other Pituitary Hormone Deficiencies
Table 14.1.5	ITT/PP	Results of Sellar MRI
Table 14.1.6	SAFETY	Prior Medications
Table 14.1.7	ITT	Summary of Protocol Deviations

13.2 EFFICACY DATA

Table 14.2.1.1	ITT/PP	Annualised height velocity by Visit: Observed Case, summary statistics
Table 14.2.1.2	ITT/PP	Annualised height velocity by Visit and Subgroup: Observed Case
Table 14.2.1.3	ITT/PP	Annualised height velocity by Visit: MMRM analysis, Observed Case
Table 14.2.1.6	ITT/PP	Annualised height velocity by Visit: Impute Missing Height Velocity after Dropout, summary statistics
Table 14.2.1.7	ITT	Annualised height velocity at by Visit: Sensitivity analysis MMRM analysis, Impute Missing Height Velocity after Dropout
Table 14.2.1.8	ITT/PP	Annualised height velocity by Visit: ANCOVA Analysis, Observed Case
Table 14.2.2.1	ITT	Height SDS by Visit: summary statistics
Table 14.2.2.2	ITT	Height SDS by Visit and Subgroup: summary statistics
Table 14.2.2.3	ITT	Change from baseline in Height SDS by visit: MMRM analysis
Table 14.2.2.4	ITT	Height Velocity SDS by Visit: summary statistics
Table 14.2.2.5	ITT	Height Velocity SDS by Visit and Subgroup: summary statistics
Table 14.2.3.1	ITT	Serum IGF-1 by Visit: summary statistics
Table 14.2.3.2	ITT	Serum IGF-1 by Visit and Subgroup: summary statistics
Table 14.2.3.3	ITT	Serum IGF-1 SDS by Visit: summary statistics
Table 14.2.3.4	ITT	Serum IGF-1 SDS by Visit and Subgroup: summary statistics
Table 14.2.3.5	ITT	Serum IGF-1 by visit: MMRM analysis
Table 14.2.3.6	ITT	Serum IGF-1 SDS by visit: MMRM analysis
Table 14.2.3.7	ITT	Normalisation of IGF-1 SDS by visit
Table 14.2.3.9	ITT	Average IGF-1 SDS at Weeks 13, 26, and 39

Table 14.2.3.10	ITT	Proportion of Subjects Achieving Normalization of IGF-1 SDS within 0 to 2.0 Based on Average IGF-1 SDS at Weeks 13, 26, and 39
Table 14.2.3.11	ITT	Average IGF-1 SDS at Weeks 13, 26, and 39 (Based on the Non-Linear Mixed Model TransCon hGH, Average for Genotropin): ANCOVA Analysis
Table 14.2.3.12	ITT	Average IGF-1 SDS at Weeks 13, 26, and 39 within 0-2.0 (Based on the Non-Linear Mixed Model TransCon hGH, Average for Genotropin): Logistic Regression Analysis
Table 14.2.4.1	ITT	Serum IGFBP-3 by Visit: summary statistics
Table 14.2.4.2	ITT	Serum IGFBP-3 by Visit and Subgroup: summary statistic
Table 14.2.4.3	ITT	Serum IGFBP-3 SDS by Visit: summary statistics
Table 14.2.4.4	ITT	Serum IGFBP-3 SDS by Visit and Subgroup: summary statistics
Table 14.2.4.5	ITT	Serum IGFBP-3 by visit: MMRM analysis
Table 14.2.4.6	ITT	Serum IGFBP-3 SDS by visit: MMRM analysis

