8.2 Secondary Efficacy Variable Analysis

The absolute values and mean change from baseline at each timepoint of other secondary efficacy endpoints will be presented by treatment group with descriptive statistics. Height velocity SDS will also be summarized. Mixed model for repeated measurement (MMRM) models will be used for the following continuous secondary efficacy endpoints. Missing data will not be imputed before conducting the MMRM model. The MMRM model for height velocity will include baseline age, peak GH levels (log transformed) at stimulation test, baseline height SDS – average SDS of parental height, as covariates, gender as a fixed factor, and subject as a random effect. The MMRM model for all the following continuous variables will include treatment, timepoint, and treatment by timepoint interaction.

- height velocity
- change in height SDS
- serum IGF-1 levels
- serum IGFBP-3 levels
- IGF-1 SDS
- IGFBP-3 SDS

The MMRM model for change in height SDS, IGF-1, IGFBP-3, IGF-1 SDS and IGFBP-3 SDS will include baseline age, peak GH (log transformed), baseline (of the corresponding variable) as covariates, and gender as a factor.

For the patients who are in PK/PD population, the average values from hour 48 and hour 72 at Visit 3 (Week 13) will be considered as the Visit 3 value for IGF-1, IGF-1 SDS, IGFBP-3 and IGFBP-3 SDS, and used in the analyses for Visit 3.

Two sided 95% confidence intervals will be calculated for the difference in least square means between the 2 treatment groups. Change from baseline will be summarized when appropriate as supportive analyses.

The rate of subjects achieving normalization of serum IGF-1 SDS will be calculated by treatment group and visit defined as SDS scores of 0 to 2.0. Additionally, cut points of -2.0 to +2.0 and -1.0 to +2.0 will be assessed. The following IGF-1 SDS variables will be derived:

- Average IGF-1 SDS at visits 3, 4, and 5
- Proportion of subjects achieving normalization of IGF-1 SDS of 0 to 2.0 based on the average IGF-1 SDS at visits 3, 4, and 5

The rates of subjects achieving IGF-1 SDS 0-2.0 will be analyzed by logistic regression adjusting for baseline age and baseline IGF-1 SDS. In case of model convergence issues caused by sparse cells, Fisher's exact test will be carried out instead.

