8.3 Average IGF-1 SDS at Week 52 based on population PK/PD modeling

Due to differences in the PD profiles of the two treatment groups, the analysis of superiority in IGF-1 SDS described in [Section 8.2](#) will be supported by the analysis of average IGF-1 SDS starting from Visit 3 (Week 13) to end of study. The average IGF-1 SDS at Week 52 group will be calculated based on the following steps:

1. A non-linear mixed model by treatment will be conducted for IGF-1 concentration data, based on rich sampling data from the Phase 2 study in growth hormone deficient pediatrics (Ascendis Pharma study no. ACP-001 CT-004), and from the rich sampling in the PK/PD population in this study, and from all sampling data at steady state (visits 3-6) from the rest of the subjects in this study.
2. The non-linear mixed model of IGF-1 concentration will be fitted to describe relationship of dose, time since dosing to IGF-1 concentration. The most simple compartment model which can sufficiently explain IGF-1 kinetics will be selected and goodness of fit will be assessed based on standard model diagnostics.
3. The weekly IGF-1 AUC (0-168 hours after dosing) will be calculated for each individual subject based on the non-linear mixed model established from Step 2.
4. The weekly average IGF-1 concentration for each subject is calculated as:
$$\text{Weekly average IGF-1 concentration} = \text{Weekly IGF-1 AUC (from Step 3)} / 168.$$
5. The average IGF-1 SDS at Week 52 is determined based on the weekly average IGF-1 concentration in Step 4 for each individual subject.

The average IGF-1 SDS at Week 52 will be analyzed by an analysis of covariance (ANCOVA) model with the same model covariate selection as described for the MMRM model in [Section 8.2](#). The proportion of subjects achieving average IGF-1 SDS within 0-2.0 will be analyzed with the same logistic regression model as described in [Section 8.2](#).

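### Tables 14.2.3.11 and 14.2.3.12 contradict SAP 8.3 on how and when average IGF-1 SDS is derived; followed as titled, they would compare the arms on different estimators.

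*SAP*

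**What the plan says.** SAP 8.3 opens its steps with "A non-linear mixed model by treatment will be conducted for IGF-1 concentration data". The data are rich samples from the phase 2 paediatric trial, rich samples from this trial's PK/PD population, "and from all sampling data at steady state (visits 3-6) from the rest of the subjects in this study". That last group is not limited to TransCon. The weekly AUC "will be calculated for each individual subject based on the non-linear mixed model" and is divided by 168 to give a weekly mean concentration. Finally, "The average IGF-1 SDS at Week 52 is determined based on the weekly average IGF-1 concentration in Step 4 for each individual subject". This value is analysed by ANCOVA, and "The proportion of subjects achieving average IGF-1 SDS within 0-2.0 will be analyzed with the same logistic regression model" as in 8.2.

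The only entries in SAP 13.2 that match these two analyses are Tables 14.2.3.11 and 14.2.3.12. Their titles name Weeks 13, 26 and 39 and end "Based on the Non-Linear Mixed Model TransCon hGH, Average for Genotropin): ANCOVA Analysis" and "Based on the Non-Linear Mixed Model TransCon hGH, Average for Genotropin): Logistic Regression Analysis" respectively.

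SAP 8.2 separately defines "Average IGF-1 SDS at visits 3, 4, and 5" and the 0-2.0 proportion based on it. Tables 14.2.3.9 and 14.2.3.10 report these with no arm-specific method.

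**The concern.** The two sections disagree on two things. The first is the estimator: 8.3 models both arms, while the titles model TransCon only. The second is the time basis: 8.3 derives a Week 52 value, while the titles name Weeks 13, 26 and 39. Section 8.3 adds a third basis, because its introduction describes an average from Week 13 through the end of the study.

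The estimator matters because of the endpoint. Individual predictions from a mixed model fitted to sparse samples are pulled toward the population mean, so they spread less than the true values. A mean of three observed visits keeps part of the visit-to-visit noise, so it spreads more. A proportion inside a two-sided range depends on spread as well as on the mean. Two arms with identical true IGF-1 distributions would then show different proportions. Adjusting for baseline age and baseline IGF-1 SDS, as the logistic model does, does not put the two arms on the same spread.

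**Working it through.** **Plan figure.** The SAP states no IGF-1 mean, variance, shrinkage or expected proportion, so there is no figure to reproduce. The sample size in SAP 3.2 concerns height velocity and is not involved.

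**Texts compared.**

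| | SAP 8.3 | Titles of 14.2.3.11 and 14.2.3.12 |
|---|---|---|
| TransCon | model-based individual average | model-based |
| Genotropin | model-based individual average | an average, apparently the observed one of 8.2 |
| Time | Week 52 (introduction: Week 13 to end of study) | Weeks 13, 26, 39 |

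**Illustration.** Everything numerical here is an assumption. Let the true SDS be normal with mean m and between-child SD b, the same in both arms. Let w be the visit SD and let there be three visits.

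- Observed mean: variance = b² + w²/3.
- Shrunken estimate: variance = R × b², with R = b²/(b² + w²/3).
- Proportion in range, for a spread s: Φ((2 − m)/s) − Φ((0 − m)/s).

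*Worked example, m = 1.0, b = 0.9, w = 0.9.*
- Observed: 0.81 + 0.27 = 1.08, s = 1.039, proportion 66.4%.
- Shrunken: R = 0.81/1.08 = 0.75; 0.75 × 0.81 = 0.6075, s = 0.779, proportion 80.1%.
- True: s = 0.9, proportion 73.3%.
- Gap: 80.1 − 66.4 = 13.7 points before further rounding. Of this, 80.1 − 73.3 = 6.8 comes from shrinkage and 73.3 − 66.4 = 6.9 from visit noise in the observed mean. Each source gives about half.

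*Range of TransCon minus Genotropin, b = 0.7-0.9.*

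| Common mean m | Visit SD w | Gap (points) |
|---|---|---|
| 0.3 to 1.0 | 0.6-0.9 | +3.5 to +17.6 |
| 0.3 to 1.0 | 0.3 | +0.9 to +2.4 |
| 0 | 0.6-0.9 | +0.5 to +2.2 |
| −0.3 | 0.6-0.9 | −1.2 to −6.4 |

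A wider grid (b 0.8-1.2, w 0.4-1.0, m −1 to 2.5) gives −9.3 to +18.8 points. The gap also turns negative when the mean is above the range (m = 2.5).

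*Same estimator and same spread in both arms:* the gap is 0.

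**Limits of the illustration.** Section 8.3 uses Visits 3-6. With four visits on the model side only, the example gap falls to 78.6 − 66.4 = 12.2 points. Section 8.3 also models concentration and then converts to SDS, so actual shrinkage will not follow this linear form exactly. In this simple model the arm mean is not shifted, so the calculation shows unequal spread, but no bias in the mean, for the ANCOVA in Table 14.2.3.11.

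**The case against.** The strongest reply is that the titles are stale and 8.3 governs. The document history records that Version 4.0 changed how 8.3 calculates the Week 52 average. The table list shows other signs of lagging: Table 14.2.1.7 still describes an MMRM on imputed height velocity, and some table numbers are skipped. Shells are kept in a separate document. If programmers follow 8.3, the one-sided artefact does not arise. This stands as a likely explanation, but nothing in the SAP says which text prevails.

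Second, TransCon needs a model. Its Visits 3-5 are sampled 48-72 hours after dosing, which the protocol ties to the IGF-1 maximum effect, so a plain visit mean would not represent its weekly average. This stands too. It justifies modelling TransCon, but not a different estimator for the comparator, and 8.3 already models both arms.

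Third, the consequence is limited. Section 8.3 is presented as support for 8.2, and the procedure in 8.6 covers only height velocity, non-inferiority then superiority. This stands.

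A reader might go further and infer that all planned IGF-1 outputs treat the arms unequally, or that the plan favours TransCon. The documents support neither. Only two tables carry the arm-specific wording, and Tables 14.2.3.9 and 14.2.3.10 already give a common-method version. The direction of any artefact depends on where the mean lies, which is not stated. That the Genotropin average is the observed Visit 3-5 mean is also an inference from the title and 8.2.

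**Conclusion.** The contradiction is definite: estimator and time basis differ between 8.3 and the two titles, and 8.3 does not settle its own time basis. The artefact is conditional. It arises only if the titles are followed, and its size and sign rest on assumed values. It is about +4 to +18 points for TransCon at a common mean of 0.3-1.0 with between-child SD 0.7-0.9 and visit SD 0.6-0.9. It is about 1-2 points if the visit SD is 0.3, and negative for a mean below the range. It should not be attributed to shrinkage alone. The primary conclusion and familywise error are untouched. The correction is still worth making before analysis, because normalization of IGF-1 SDS is a listed secondary endpoint and the choice of text could change the reported comparison.

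**What to change.** - Use the 8.3 model-based weekly average in both arms, and retitle Tables 14.2.3.11 and 14.2.3.12 to say so.
- State one time basis, in the same words, in the introduction to 8.3, in its final step and in the two titles.
- Report shrinkage of the individual estimates by arm. Rich sampling in this trial is in TransCon only, so fitting the model in both arms need not equalise shrinkage. Tables 14.2.3.9 and 14.2.3.10 can be read alongside as the common-method comparison on observed values.

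The cost is SAP wording, two titles and a short diagnostic output. The Genotropin model fit is already called for in 8.3, and no new data are needed.

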13.3 SAFETY DATA

14.3.1 Displays of Adverse Events

Table 14.3.1.1	SAFETY	Summary of Adverse Events
Table 14.3.1.2	SAFETY	Treatment Emergent Adverse Events: Incidences by Preferred Term
Table 14.3.1.3	SAFETY	Treatment Emergent Adverse Events: Incidences by System Organ Class and Preferred Term
Table 14.3.1.4	SAFETY	Treatment Emergent Adverse Events by Strongest Relationship (CRF Categories) to Study Drug: Incidences by System Organ Class and Preferred Term
Table 14.3.1.5	SAFETY	Treatment Emergent Adverse Events by Maximum Severity of Event: Incidences by System Organ Class and Preferred Term
Table 14.3.1.6	SAFETY	Treatment Emergent Adverse Events leading to Withdrawal of Study Drug: Incidences by System Organ Class and Preferred Term

14.3.2 Summary of Deaths, Other Serious and Significant Adverse Events

Table 14.3.2.1	SAFETY	Serious Adverse Events: Incidences by System Organ Class and Preferred Term
Table 14.3.2.2	SAFETY	Summary of Related Treatment Emergent Adverse Events Leading to Discontinuation of Study Drug: Incidences by System Organ Class and Preferred Term
Table 14.3.2.3	SAFETY	Summary of Unrelated Treatment Emergent Adverse Events Leading to Discontinuation of Study Drug: Incidences by System Organ Class and Preferred Term

14.3.3 Laboratory Data Summary Tables

Table 14.3.3.1.1	SAFETY	Summary of Central Laboratory Data - Hematology by Visit (Conventional Units)
Table 14.3.3.1.2	SAFETY	Summary of Central Laboratory Data - Hematology by Visit (SI Units)
Table 14.3.3.2	SAFETY	Central Laboratory Data - Hematology: Assessments (SI Units) by Visit
Table 14.3.3.3	SAFETY	Central Laboratory Data - Hematology: Shift in Assessments Compared to Baseline (SI Units)
Table 14.3.3.4.1	SAFETY	Summary of Central Laboratory Data - Biochemistry by Visit (Conventional Units)
Table 14.3.3.4.2	SAFETY	Summary of Central Laboratory Data - Biochemistry by Visit (SI Units)
Table 14.3.3.5	SAFETY	Central Laboratory Data - Biochemistry: Assessments by (SI Units) Visit
Table 14.3.3.6	SAFETY	Central Laboratory Data - Biochemistry: Shift in Assessments Compared to Baseline (SI Units)
Table 14.3.3.7.1	SAFETY	Summary of Central Laboratory Data – Glucose Metabolism by Visit (Conventional Units)
Table 14.3.3.7.2	SAFETY	Summary of Central Laboratory Data - Glucose Metabolism by Visit (SI Units)
Table 14.3.3.8	SAFETY	Central Laboratory Data - Glucose Metabolism: Assessments (SI Units) by Visit
Table 14.3.3.9	SAFETY	Central Laboratory Data - Glucose Metabolism: Shift in Assessments Compared to Baseline (SI Units)
Table 14.3.3.10.1	SAFETY	Summary of Central Laboratory Data – Lipid Metabolism by Visit (Conventional Units)
Table 14.3.3.10.2	SAFETY	Summary of Central Laboratory Data - Lipid Metabolism by Visit (SI Units)
Table 14.3.3.11	SAFETY	Central Laboratory Data - Lipid Metabolism: Assessments (SI Units) by Visit
Table 14.3.3.12	SAFETY	Central Laboratory Data - Lipid Metabolism: Shift in Assessments Compared to Baseline (SI Units)
Table 14.3.3.13.1	SAFETY	Summary of Central Laboratory Data – Hormone Status by Visit (Conventional Units)
Table 14.3.3.13.2	SAFETY	Summary of Central Laboratory Data - Hormone Status by Visit (SI Units)
Table 14.3.3.14	SAFETY	Central Laboratory Data - Hormone Status: Assessments (SI Units) by Visit
Table 14.3.3.15	SAFETY	Central Laboratory Data - Hormone Status: Shift in Assessments Compared to Baseline (SI Units)
Table 14.3.3.16.1	SAFETY	Summary of Antibodies
Table 14.3.3.16.2	SAFETY	Summary of Antibodies by visit

